### **8.3 Sample Size**

The required sample size ranges from 11 to 48 evaluable subjects. In the event that 5% of subjects are not evaluable for objective response evaluation, the maximum sample size is 50 subjects.

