## 1.0 TRIAL SUMMARY

Title:	Phase II study of Pembrolizumab and Itacitinib (INCB039110) for First Line Treatment of Metastatic Non-Small Cell Lung Cancer Expressing PD-L1
Abbreviated Title	Pembrolizumab and itacitinib (INCB039110) for NSCLC
Protocol Numbers	UPCC#09517; IRB#828910; NCT03425006; IND#137721
Trial Phase	Phase II
Study Center(s)	University of Pennsylvania
Study Population	The first line treatment of patients with metastatic PD-L1 positive non-small cell lung cancer (NSCLC)
Methodology	This is a single center, single arm phase 2 study to establish the safety and efficacy of itacitinib (also known as INCB039110) administered in combination with pembrolizumab in patients with metastatic PD-L1 positive non-small cell lung cancer (NSCLC).
Study Drugs, Dose and Regimen	
Study Drug(s)
 

• Itacitinib: a JAK 1 selective small molecule inhibitor; an investigational agent that is study supplied

• Pembrolizumab: a highly selective humanized monoclonal antibody (mAb)

 
Dose and Route of Administration
 

• Itacitinib: 200mg PO (extended release formulation)

• Pembrolizumab: 200mg IV infusion over 30 minutes

 
Regimen
 

• Treatment = 3 week (Q3W) dosing cycles

• Itacitinib: Once daily for Cycle 3 and Cycle 4 (up to 6 weeks)

• Pembrolizumab: Q3 week cycles of treatment beginning at Day 1; if the PI considers it beneficial for the subject, a fifth cycle may be administered prior to EOS visit.

Number of trial subjects	Up to 48 evaluable subjects
Estimated duration of trial	Approximately 48 months

CONFIDENTIAL

This material is the property of the University of Pennsylvania. Do not disclose or use except as authorized in writing by the study sponsor.

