## 2.0 TRIAL DESIGN

### 2.1 *Trial Design*

This is an optimal 3-stage Phase II trial of pembrolizumab and itacitinib for first line treatment of PD-L1 positive metastatic NSCLC. Up to 48 evaluable subjects will be enrolled to examine the efficacy of adding itacitinib to pembrolizumab among patients with previously untreated metastatic NSCLC with tumor PD-L1 expression greater than or equal to 50%. Subjects will receive 2 cycles of pembrolizumab (200mg every 3 weeks), and then undergo repeat imaging and tumor biopsy. Beginning on the Day 1 of Cycle 3 the subject will receive itacitinib (selective JAK1 inhibitor) 200 mg daily for 6 weeks. Pembrolizumab will be continued at the same dose and frequency. After 6 weeks of treatment (week 12 of treatment overall) with itacitinib, repeat imaging and tumor biopsy will be performed. The scan is purely for biopsy planning, and no treatment decisions will be made based upon the results ([Figure 1](#)). Objective response by RECIST 1.1 will be determined based on the week 12 scan. Subjects who either experience documented progressive disease during the first 12 weeks of treatment or complete the first 12 weeks of treatment and undergo re-staging (i.e., PET/CT scan) will be considered evaluable for objective response evaluation. Subjects who are withdrawn from study (due to toxicity or other reasons) in the first 12 weeks of treatment and who do not undergo re-staging will be considered unevaluable for objective response evaluation but will be included in the safety analyses. These subjects will be replaced. Objective response rate (ORR) is defined as the proportion of evaluable subjects who achieve a complete or partial response according to RECIST 1.1 criteria.

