## **5.8 Subject Replacement Strategy**

Subjects who either experience documented progressive disease during the first 12 weeks of treatment or complete the first 12 weeks of treatment and undergo re-staging are considered evaluable and will not be replaced. Subjects who complete study treatments but are unable to complete planned biopsies will also be considered evaluable for response and adverse events. All other subjects will be considered non-evaluable and will be replaced.

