## **8.0 STATISTICAL ANALYSIS PLAN**

### ***8.1 Statistical Design***

**3-stage optimal design.** The ORR for pembrolizumab in untreated PD-L1 positive advanced NSCLC was recently reported (Reck NEJM Oct 2016) to be 45% (95% CI 37-53%). The 3-stage optimal design (TT Chen, Statistics in Medicine 16:2701-2711,1997) tests the null hypothesis that the  $ORR \leq 35\%$  (clearly inferior to pembrolizumab) versus the alternative that the  $ORR \geq 55\%$  (clearly superior to pembrolizumab). Eleven evaluable subjects will be entered into the first stage of the study. If 2 or fewer of these 11 subjects respond, then the trial will be terminated. If at least 3 of these subjects respond, then an additional 19 evaluable subjects will be entered into the second stage of the study. If 12 or fewer of these 30 subjects respond, then the trial will be terminated. If at least 13 of these subjects respond, then an additional 18 evaluable subjects will be entered into the third stage of the study. If 20 or fewer of these 48 subjects respond, then it will be concluded that the regimen does not merit further investigation. If at least 21 of these 48 subjects respond, then it will be concluded that the regimen merits further investigation. If the true objective response rate is 35%, then the probability of recommending the regimen for further investigation (false positive error), is 0.100. While if the true objective response rate is 55%, then the probability of recommending the regimen for further investigation (power), is 0.906. If the true objective response rate is 35%, then the probability of early termination of the trial by the end of the second stage is 0.786. The software program, PASS v14 was employed to define this 3-stage design.

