### ***8.2 Statistical Analysis Plan***

Based on evaluable subjects, the objective response rate and 95% confidence interval will be calculated. Duration of remission, progression-free survival and overall survival will be estimated by the method of Kaplan and Meier. Median values and 95% confidence intervals will be calculated. All observed toxicities will be graded and tabled. Toxicity tables will be separately constructed for cycles with pembrolizumab alone (cycles 1-2 and cycle  $\geq 5$ ) or pembrolizumab and itacitinib (cycles 3-4). Changes in immune pharmacodynamic biomarkers will be examined with scatter plots and summary statistics. Fold changes from baseline values will be estimated and summarized. **Sample Size:** The required sample size ranges from 11 to 48 evaluable subjects. In the event that 5% of subjects are not evaluable for objective response evaluation, the maximum sample size is 50 subjects. **Study Duration:** With an estimated accrual of 2 patients per month, it is anticipated that accrual will continue for approximately 24 months and subject follow-up will continue for up to year post Cycle 1/Day 1 (initiation of study treatment) for a total study duration of up to 36 months.

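### The stated maximum of 50 subjects is one too few for 48 evaluable at the plan's own 5% unevaluable rate (48/0.95 rounds up to 51) and, read as a limit, conflicts with the replacement rule (minor)

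*Combined protocol and SAP*

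**What the plan says.** The design counts evaluable subjects throughout. The Trial Summary (section 1.0) gives the number of subjects as "Up to 48 evaluable subjects", and section 8.3 says "The required sample size ranges from 11 to 48 evaluable subjects". The stage rules in section 8.1 are set at 11, 30 and 48 evaluable subjects: "If 2 or fewer of these 11 subjects respond, then the trial will be terminated"; "If 12 or fewer of these 30 subjects respond, then the trial will be terminated"; and at the end, 21 or more responses among 48 count as success. The stated false positive error is 0.100 at a true objective response rate (ORR) of 35%, and the stated power is 0.906 at 55%.

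Section 8.3 then allows for subjects who cannot be evaluated: "In the event that 5% of subjects are not evaluable for objective response evaluation, the maximum sample size is 50 subjects". The sample-size text inside section 8.2 ends the same way: "the maximum sample size is 50 subjects".

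Two other sections deal with the same subjects. Section 2.1 says of those withdrawn in the first 12 weeks without re-staging: "These subjects will be replaced". Section 5.8, having defined who is evaluable, says: "All other subjects will be considered non-evaluable and will be replaced". Neither section limits the number of replacements.

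**The concern.** There are two faults, both small.

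The first is arithmetic. A total that allows for 5% unevaluable should yield the evaluable number required, and 50 does not quite yield 48.

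The second is that the plan gives two instructions without ranking them. Sections 8.2 and 8.3 call 50 a maximum, while sections 2.1 and 5.8 replace without limit. If stage 3 is reached and a third subject among the first 50 is unevaluable, both cannot be followed, and no passage says which governs.

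What would be at stake is the final decision rule. Section 8.1 defines it for exactly 48 evaluable subjects. If accrual did stop at 50 with 47 or fewer evaluable, the protocol would give no cut-off, and one would have to be chosen in an open-label trial after responses were known.

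**Working it through.** **Inputs.** From sections 8.1 to 8.3: 48 evaluable subjects at most; 5% unevaluable; a total of 50; stages at 11, 30 and 48 evaluable; stop at 2 or fewer, then at 12 or fewer; success at 21 or more. Assumption for the probabilities: each subject is unevaluable independently with probability 0.05, and this is unrelated to the decision to go on to stage 3.

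**Step 1: the plan's operating characteristics.** Exact binomial enumeration of the three stages gives:

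| Quantity | Stated | Recomputed |
|---|---|---|
| False positive error, ORR 35% | 0.100 | 0.0997 |
| Power, ORR 55% | 0.906 | 0.9057 |
| Stopped by end of stage 2, ORR 35% | 0.786 | 0.7857 |

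The design itself is sound at 48 evaluable.

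**Step 2: the total of 50.**
- Required total = 48/(1 − 0.05) = 50.53, rounded up to 51.
- Expected evaluable from 50 = 50 × 0.95 = 47.5, which is below 48.
- Expected evaluable from 51 = 51 × 0.95 = 48.45.
- Multiplying instead, 48 × 1.05 = 50.4. This becomes 50 only if a requirement is rounded to the nearest whole number rather than up.

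The stated figure is therefore one subject short, or 2%.

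**Step 3: what follows only if 50 were a hard cap and stage 3 were reached.** With X unevaluable among 50, X ~ Bin(50, 0.05):

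P(X ≥ 3) = 1 − 0.5405 = 0.459.

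The shortfall cannot occur in a trial that stops earlier, so it must be multiplied by the chance of reaching stage 3:

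| True ORR | P(reach stage 3) | × 0.459 = overall shortfall |
|---|---|---|
| 35% | 0.214 | about 10% |
| 45% | 0.630 | about 29% |
| 55% | 0.922 | about 42% |

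**Step 4: effect on error and power in that case.** Keep the 11- and 30-subject stages, shorten stage 3, and keep the cut at 21:
- With 47 evaluable: error 0.087, power 0.897.
- Averaged over the binomial number evaluable among 50 (capped at 48): error about 0.089, power about 0.896.

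If the cut were lowered to 20 at 47 evaluable, the error would be 0.123, above the stated 0.100. That is why the choice should not be left open.

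**Step 5: would a cap of 51 cure it?** No. The chance of fewer than 48 evaluable would be 0.251 with a cap of 51, 0.117 with 52 and 0.048 with 53. A fixed total near the expected count will often fall short, so 51 serves as an expected total and not as a new ceiling.

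**The case against.** The strongest reply is that 50 was never meant as a cap. The sentence is conditional on a 5% scenario and follows directly on one that states the requirement in evaluable subjects. Every stage is defined the same way, and unevaluable subjects are replaced. On that reading accrual simply continues to 48 evaluable, the rule of 21 among 48 applies, and the stated error and power hold. The discrepancy is then one subject, from not rounding up. This stands, and it is why the point is minor. It does not make 50 right: as a projection at 5% the figure is still 51, and the word maximum still says something the replacement rule does not.

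A reader might infer from the same figures that the trial will miss its 48 evaluable subjects nearly half the time, or that it is underpowered. The documents do not support either inference. No passage stops accrual at 50. The 46% needs both an enforced cap and a trial that reaches stage 3. Even then average power falls by about one percentage point, and the false positive error falls too. Nor do the documents state a separate power target that this loss would breach; they report only the 0.906 the design achieves.

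It might also be argued that the real unevaluable rate will exceed 5%. The documents give no other rate, so a higher one would be an outside assumption, and the point does not need it.

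**Conclusion.** Minor, but wrong as written. At 5% unevaluable, 48 evaluable subjects require 51 treated, not 50. As a maximum, 50 also contradicts the unlimited replacement in sections 2.1 and 5.8.

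The arithmetic rests only on the plan's own 48 and 5%. The 46%, the overall 10%, 29% and 42%, and the averaged power and error rest on three further assumptions: 50 enforced as a hard cap, independent 5% non-evaluability, and the cut of 21 kept. The documents establish none of these, so those figures show what a hard-cap reading would cost and are not the trial's expected behaviour. The stage boundaries and the stated error and power at 48 evaluable need no change.

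**What to change.** In sections 8.2 and 8.3, replace the sentence giving the maximum of 50 with wording such as: *Accrual continues, with replacement per section 5.8, until up to 48 subjects are evaluable; at 5% unevaluable, about 51 treated subjects are expected.* Drop the word maximum for the treated total.

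If the sponsor does want a firm ceiling on treated subjects, the plan should say that it overrides replacement, and should fix in advance the final cut-off for fewer than 48 evaluable, with its error and power.

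The first option is a wording change in two places. It adds about one subject to the stated figure and none beyond what the replacement rule already requires.

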## **9.0 LABELING, PACKAGING, STORAGE AND RETURN OF STUDY DRUGS**

### **9.1 *Itacitinib***

#### **9.1.1 Availability**

Study drug supplied by Incyte. Provided as 100 mg (free base equivalent) sustained-release tablets.

#### **9.1.2 Preparation**

None

#### **9.1.3 Storage and Stability**

Itacitinib should be stored in a secure, limited-access location at ambient conditions (15°C to 30°C, or 59°F to 86°F).

#### **9.1.4 Product Handling and Labeling**

The investigator shall take responsibility for and shall take all steps to maintain appropriate records and ensure appropriate supply, storage, handling, distribution and usage of investigational product in accordance with the protocol and any applicable laws and regulations.

Receipt and dispensing of trial medication must be recorded by an authorized person at the trial site. All study drug dispensed will be affixed with a clinical label in accordance with regulatory requirements. Subjects will be instructed to bring all used/unused study medications to the site at each study visit. Subjects will also be asked to document administration on a study-supplied pill diary.

Clinical supplies may not be used for any purpose other than that stated in the protocol.

#### **9.1.5 Potential Toxicities**

Please refer to the itacitinib Investigator Brochure.

### **9.2 *Pembrolizumab***

Commercially available and administered per package insert with the exception of the drug will be administered with another drug, itacitinib. Please refer to the pembrolizumab package insert for additional information.

### **9.3 Returns and Reconciliation (*Itacitinib*)**

The investigator is responsible for keeping accurate records of the clinical supplies received from Incyte, the amount dispensed to and returned by the subjects, and the amount remaining at the conclusion of the trial.

CONFIDENTIAL

This material is the property of the University of Pennsylvania. Do not disclose or use except as authorized in writing by the study sponsor.

Upon completion or termination of the study, all unused and/or partially used investigational product will be destroyed and/or returned as per instructions from the sponsor. It is the Investigator's responsibility to arrange for appropriate disposal according to applicable federal, state, local and institutional guidelines and procedures, and maintain appropriate records of disposal.

## 10.0 SAFETY AND ADVERSE EVENTS

### 10.1 *Definitions*

#### Adverse Event

An **adverse event (AE)** is any untoward medical occurrence associated with the use of a drug in humans, whether or not considered drug related. Intercurrent illnesses or injuries should be regarded as adverse events.

#### Serious Adverse Event

Adverse events are classified as serious or non-serious. A **serious adverse event** is any AE that is:

- fatal
- life-threatening
- requires or prolongs hospital stay
- leads to a persistent or significant disability or incapacity or substantial disruption of the ability to conduct normal life functions
- a congenital anomaly or birth defect
- an important medical event

Hospitalizations that meet the following criteria should not be reported as serious adverse events:

- Routine treatment or monitoring of the studied indication, not associated with any deterioration in condition, such as preplanned study visits and preplanned hospitalizations for study procedures or treatment administration
- Elective or pre-planned treatment for a pre-existing condition that is unrelated to the indication under study and has not worsened since signing the informed consent
- Social reasons and respite care in the absence of any deterioration in the patient's general condition

Note: Treatment on an emergency outpatient basis that does not result in hospital admission and involves an event not fulfilling any of the definitions of a SAE given above is not a serious adverse event.

Important medical events are those that may not be immediately life threatening, but are clearly of major clinical significance. They may jeopardize the subject, and may require intervention to prevent one of the other serious outcomes noted above. For example, drug overdose or abuse, a seizure that did not result in in-patient hospitalization, or intensive treatment of bronchospasm in an emergency department would typically be considered serious.

All adverse events that do not meet any of the criteria for serious should be regarded as **non-serious adverse events**.

CONFIDENTIAL

This material is the property of the University of Pennsylvania. Do not disclose or use except as authorized in writing by the study sponsor.

### **Unexpected adverse events**

An adverse event is considered unexpected if the event, the severity of the event (grade), and/or the frequency of the event is not consistent with the risk information described in the investigator brochure, package insert, or protocol. Please refer to the itacitinib investigator brochure and pembrolizumab package insert for additional detail related to severity and/or frequency of a particular event.

### **Related adverse events**

An adverse event is considered related to participation in the research if there is a reasonable possibility that an event was caused by an investigational product, intervention, or research-required procedures. For the purposes of this study, "reasonable possibility" means there is evidence to suggest a causal relationship. The relationship of the event to the study will be classified as possibly related, probably related, and definitely related.

- **Possibly Related:** There is some evidence to suggest a causal relationship, however other factors may have contributed to the event.
- **Probably Related:** There is evidence to suggest a causal relationship, and the influence of other factors is unlikely.
- **Definitely Related:** There is clear evidence to suggest a causal relationship, and other possible contributing factors can be ruled out.

### **Adverse Event Reporting Period**

Collection of adverse events will begin at the time of consent and continue through the End of Study Visit.

After the End of Study Visit, any SAE that the investigator becomes aware of must be reported to the sponsor if the investigator suspects the event may reasonably be related to the study treatment.

### **Preexisting Condition/General Physical Examination Findings**

A preexisting condition is one that is present prior to the start of the Adverse Event Reporting Period. All clinically significant abnormalities should be recorded as a preexisting condition on the medical history eCRF. During the course of the study, a preexisting condition should be recorded as an adverse event if the frequency, intensity, or the character of the condition worsens. Preexisting conditions that improve should also be recorded appropriately.

### **Abnormal Laboratory Values**

A clinical laboratory abnormality should be documented as an adverse event if any one of the following conditions is met:

- The laboratory abnormality is not otherwise refuted by a repeat test to confirm the abnormality
- The abnormality suggests a disease and/or organ toxicity
- The abnormality is of a degree that requires active management; e.g. change of dose, discontinuation of the drug, more frequent follow-up assessments, further diagnostic investigation, etc.

Laboratory abnormalities that meet the criteria for Adverse Events should be followed until they have returned to normal or an adequate explanation of the abnormality is found. When an abnormal laboratory or test result corresponds to a sign/symptom of an already reported adverse

CONFIDENTIAL

This material is the property of the University of Pennsylvania. Do not disclose or use except as authorized in writing by the study sponsor.

event, it is not necessary to separately record the lab/test result as an additional event. Laboratory abnormalities that do not meet the definition of an adverse event, should not be reported as adverse events. A Grade 3 or 4 event (severe) as per CTCAE does not automatically indicate a SAE unless it meets the definition of serious defined above and/or as per investigator's discretion. Whenever possible, a diagnosis, rather than a symptom should be provided (i.e. anemia instead of low hemoglobin).

## **10.2 Recording of Adverse Events**

Safety will be assessed by monitoring and recording potential adverse effects of the treatment using the Common Terminology Criteria version 5.0 at each study visit. Patients will be monitored by medical histories, physical examinations, and blood studies to detect potential toxicities from the treatment. If CTCAE grading does not exist for an adverse event, the severity of mild, moderate, severe, life-threatening, and death, corresponding to Grades 1-5, will be used whenever possible. Subjects will be monitored by medical histories, physical examinations, and blood studies to detect potential toxicities from the treatment.

At each contact with the subject, the investigator must seek information on adverse events by non-directive questioning and, as appropriate, by examination. Adverse events also may be detected when they are volunteered by the subject during the screening process or between visits, or through physical examination, laboratory test, or other assessments. Information on all adverse events should be recorded in the source documentation. All clearly related signs, symptoms, and abnormal diagnostic procedures results should be recorded in the source document, though should be grouped under one diagnosis. To the extent possible, adverse events should be recorded as a diagnosis and symptoms used to make the diagnosis recorded within the diagnosis event. Do not list symptoms separately if a diagnosis can be assigned. The safety team may require events be reported separately if they occur as SAEs (or in the context of a SAE) even if they can also be considered a constituent of another AE.

All adverse events occurring during the adverse event reporting period (defined in [Section 10.1](#) above) must be recorded. Adverse events that begin during the study treatment phase, and are ongoing at the time the subject enters the survival follow-up phase of the study, will continue to be followed in survival follow-up until: a) the adverse event resolves; b) the subject discontinues participation (i.e. End of Study); or c) there is a change in the adverse event that would normally require the event be captured as a new event (i.e. change in attribution). Please refer to the CRF Completion Guidelines (CCG) for specific instructions on data entry.

As much as possible, each adverse event should be evaluated to determine:

1. The severity grade (CTCAE Grade 1-5)
2. Its duration (Start and end dates)
3. Its relationship to the study treatment- [Reasonable possibility that AE is related: No (unrelated/ not suspected) or Yes (a suspected adverse reaction)]. If yes (suspected)- is the event possibly, probably or definitely related to the investigational treatment?
4. Expectedness to study treatment- [Unexpected- if the event severity and/or frequency is not described in the investigator brochure (if applicable) or protocol].
5. Action taken with respect to study or investigational treatment (none, dose adjusted, temporarily interrupted, permanently discontinued, unknown, not applicable)
6. Whether medication or therapy taken (no concomitant medication/non-drug therapy, concomitant medication/non-drug therapy)

CONFIDENTIAL

This material is the property of the University of Pennsylvania. Do not disclose or use except as authorized in writing by the study sponsor.

7. Whether it is serious, where a serious adverse event (SAE) is defined as in **Section 10.1**.

All adverse events should be treated appropriately. If a concomitant medication or non-drug therapy is given, this action should be recorded. Once an adverse event is detected, it should be followed until its resolution or until it is judged to be permanent, and assessment should be made at each visit (or more frequently, if necessary) of any changes in severity, the suspected relationship to the study treatment, the interventions required to treat it, and the outcome.

Progression of malignancy, documented appropriately in the medical records, should not be reported as a serious adverse event. Adverse events that occur concurrently with the progression of malignancy but that are not related to disease progression (i.e. deep vein thrombosis or hemoptysis) will be reported as an adverse event as described above. Progression of malignancy resulting in death that occurs during the study treatment phase should not be reported as a serious adverse event.

Serious adverse events that are still ongoing at the end of the adverse event reporting period must be followed to determine the final outcome. Any serious adverse event that occurs after the adverse event reporting period and is considered to be possibly related to the study treatment or study participation, should be recorded and reported.

